4. STUDY-WIDE NUMBER OF PARTICIPANTS

See 23. Local Number of Subjects

5. STUDY-WIDE RECRUITMENT METHODS

See 22. Recruitment Methods

6. MULTI-SITE RESEARCH

Data will only be collected over the phone by Northwestern research staff. The provider survey, will have an email and pen and paper version available.

UNC will be home to key research collaborators who will be involved in the study design, intervention development, and interpretation of results, but will not interact with patients and will not have access to data.

Boston Medical Center (BMC) will facilitate the IVR component of the intervention. A data use agreement has been established between NU and BMC to this effect, and the Office of the Institutional Review Board at BMC has approved the transfer process proposed (described in 11.3).

STU#: 00201638

Weekly meetings with all sites (Northwestern, BMC, Alliance, UNC, UIC) will be held throughout the study. This time will be used to discuss progress of the study and any changes to the protocol or study battery. The project manager will email any modifications to the IRB protocol to the team within one day of receiving approval. The project manager will hold weekly meetings with project staff to ensure that the protocol is being followed.

7. STUDY TIMELINES

An individual patient subject will be involved in the study for a total of up to 3 months. They will complete a screener enrollment interview, a baseline interview as soon as possible following the screener, a possible follow-up interview at 4 weeks, and a possible final interview at 3 months. The need for follow-up interviews will be determined by a patient’s medication fill and take behavior (if they do not plan to fill or take the medicine or have already stopped taking the medicine, we will not need to continue with follow-up interviews). All interviews will be conducted over the phone.

We anticipate that patient enrollment will actively take place over 2 years. The date by which we expect to complete primary analyses is August 31, 2019.

Our proposed/anticipated study timeline is below:

Table 2. Study Timeline TASKS	Y1				Y2				Y3				Y4	
	1	2	3	4	1	2	3	4	1	2	3	4	1	2
PREPARATION PHASE:														
Organize research team, convene DSMB	■	■												
Translate study materials	■	■												
Protocol development	■	■												
Prepare and refine EHR tools	■	■												
Prepare and refine IVR tools	■	■												
Site orientation, training, logistics planning				■										
Prescriber randomization				■										
Integrate, pilot, debug EMC ²				■										
IMPLEMENTATION PHASE:														
Implement EMC ² Strategy				■										
Recruit, consent participants				■	■	■	■	■	■	■	■			
Conduct baseline interviews				■	■	■	■	■	■	■	■			
Conduct 2 week and 3 month interviews				■	■	■	■	■	■	■	■			
Seek process feedback from clinical staff				■			■						■	
EVALUATION PHASE:														
Clean & analyze data						■	■	■	■	■	■	■	■	■
Summarize and interpret findings								■	■	■	■	■	■	■
Provide feedback to sites, review scalability								■					■	■
Submit manuscripts for publication								■					■	■
Present findings at national venues								■	■				■	■

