8. STUDY ENDPOINTS

8.1 Primary and secondary study endpoints.

The study’s primary endpoints are medication knowledge and medication behavior (fill, proper use, and actual use).

8.2 Primary or secondary safety endpoints.

The study’s safety endpoints include assessment of any Adverse Drug Events (ADE).

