9.1 Study design

We will conduct a 2-arm, randomized trial at one Alliance-affiliated federally qualified health center (FQHC) in Chicago, Near North Health Services Corporation, to evaluate the EMC2 intervention strategy compared to usual care.

We will assess patients' Rx knowledge and behavior at baseline, 4 weeks, and 3 months. Prevalence of ADEs and rate of their detection will be determined at 3 months or at an earlier interview if they state having already completed the course of medication. The fidelity and economic impact of the intervention will also be investigated via process and cost measures, in addition to patient and provider feedback. Results will determine effectiveness and identify any necessary modifications, guiding future dissemination efforts.

Study Arms:

Usual Care. Current usual care includes 1) variable physician and/or nurse counseling without any EHR notifications or counseling support; 2) no distribution of print medication information materials in Alliance clinics, and variable, limited distribution likely in pharmacies; 3) no active surveillance of medication use post-visits.

Intervention Arm: EMC2 Strategy. Following a patient's movement through a provider visit at one of the Near North clinics randomized to the intervention, the following five activities (described in more detail in 9.2) will occur:

- Provider counseling (prompted by provider medication alert)*
- Automated delivery of med guide summary*
- IVR follow-up phone assessment
- IVR lab report to clinic via EHR
- Nurse counseling (if warranted by lab report)

**Because the first two activities must occur at the time of the clinic visit, which is before we will have the opportunity to invite the participant to enroll in the study, those activities will occur for all patients prescribed a study medication at an intervention clinic, regardless of whether or not they subsequently enroll. (see last paragraph of 3.1)*

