9.2 Description of the intervention

1. Provider Medication Alert: If a prescribing clinician attempts to place a new order or change an existing prescription for one of the study medications (Table 1), an EHR-generated alert will notify the provider that the medication requires patient counseling. This alert will contain a brief description of the top risks or side effects that patients may experience while taking this medication; this information is directly derived from the FDA-approved Medication Guide for the drug. The pop-up will also include an html link to the 1-page Med Sheet, which they can use to further inform their counseling.

2. Automated Delivery of Med Guide Summary: When the patient leaves an encounter and checks out, the medication order in Centricity will automatically cue printing of the 1-page Med Guide Summary.

STU#: 00201638

3. IVR Follow-Up Phone Assessment: One day after a patient's baseline interview (which will occur within 1-30 days post-visit), the patient will be prompted to call into the automated IVR system. The goal of the IVR call is to confirm patients' understanding and safe use of the prescribed high-risk medication they are taking, and to screen for any adverse drug events that may arise from having taken the medicine.

The call will investigate content areas that will be standard across all medications under study: 1) medication recognition, 2) medication fill (and fill barriers, if applicable), medication adherence (and adherence barriers, if applicable), perceived effectiveness, and side effects experienced. The IVR content was derived from the Med Guide Summaries. Patients are able to speak their responses as "yes", "no", or "do not know" or use their keypad.

To facilitate the call, patients will be sent (via text or phone call) a call-in number for the IVR system so that they are able to make the call at their convenience. The text with the call-in number will be sent on the day following the patient's baseline interview. (The day lag is needed so that the participant's medication data can first be uploaded to the IVR system in preparation for the call).

If subjects have not used the system after one day, a reminder text message, again including the call-in number, will be sent by the RA at Northwestern. If subjects have not used the system after two days, the RA at Northwestern will call the patient to remind them to call into the system and to ensure they have the call-in details.

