9.3 Research procedures

Research activities will include a baseline interview and follow-up interviews at 4 weeks and 3 months; all interviews will be conducted over the phone. Patients in the intervention arm will receive a prompt to call into an interactive voice response (IVR) system one day after their baseline interview (so 2-45 days after their index clinic visit) to confirm understanding and safe use of their medicine (described in 9.2 Description of the Intervention).

Pilot Testing. We will pilot-test the study battery, protocol and patient materials among English and Spanish-speaking patients at Alliance sites. Cognitive interviews will be conducted among a convenience sample of 30 patients (n=15 per language) that meet full eligibility criteria. We will obtain average interview completion times, elicit patient comprehension, and acceptability of the interview and patient materials. Any identified problems will be analyzed and modifications made as appropriate. Pilot patient data will be used if no significant changes are made to the study.

STU#: 00201638

Initial Interview. After confirming patient eligibility, obtaining verbal consent, and receiving patient prescription information, the RA will administer the baseline interview via phone. As long as the patient is still taking or planning to take the prescribed medicine, the patient will then be eligible for follow-up interviews and, if in the intervention arm, to receive the remaining EMC2 components (IVR, nurse follow-up).

Follow-up Interview #1. The first follow-up interview will be scheduled at the time of the baseline interview for 4 weeks later.

Follow-up Interview #2. The second follow-up interview will be scheduled at the time of the 4-week interview for 8 weeks later.

Spanish Language Materials. All study materials (screener script, consent form, battery, IVR call) have been or will be translated into Spanish to accommodate Spanish speakers. Several of the measures in the battery already have validated Spanish versions; everything else has been translated by Research Support Services, led by [name], using a modified committee approach. In this translation approach, three bilingual, bicultural translators independently translate one-third of each document into Spanish, then discuss the resulting texts and reach an agreement on best words/phrases for the final product. The strength of this approach has been recognized by the Census Bureau Guidelines for Survey Translation.

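### Follow-up interviews end by rule for patients not taking the drug, so 3-month knowledge is missing in a post-randomisation subset that the missing-data plan does not name

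*Combined protocol and SAP*

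**What the plan says.** **The rule.** Section 7 makes the 4-week and 3-month interviews depend on fill and take behaviour. They are dropped for patients who will not fill or use the drug, and for those who "have already stopped taking the medicine, we will not need to continue with follow-up interviews". Section 9.3 gives the same condition from the other side: "As long as the patient is still taking or planning to take the prescribed medicine", the patient stays eligible for follow-up interviews and, in the intervention arm, for the interactive voice response (IVR) call and nurse follow-up. Section 22.4 allows the final interview to fall at baseline or 1 month, with some later measures brought forward but not listed.

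**Timing.** Counselling and the Med Guide Summary come at the clinic visit; Section 9.1 says that "those activities will occur for all patients prescribed a study medication at an intervention clinic". Section 9.2 puts the baseline interview 1 to 30 days later and the IVR prompt a day after that, in the intervention arm only. The IVR call asks about fill barriers, adherence barriers and side effects, and a flagged answer can lead to a nurse response.

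**Outcome and analysis.** Section 8.1 makes knowledge and medication behaviour, including fill and actual use, the primary endpoints. Section 9.1 schedules "Rx knowledge and behavior at baseline, 4 weeks, and 3 months". Section 11.2 sizes the trial on knowledge at the 3-month interview. Section 11.1 plans a generalised linear mixed model (GLMM) on all observations with treatment by time. It notes that such models can handle data missing at random (MAR), and adds a logit model to look for predictors of missingness. If predictors are found, multiple imputation follows as a secondary analysis. Fill/take status is not listed as a covariate, missingness predictor or imputation variable.

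**The concern.** The event that ends observation is itself an outcome of the trial. Every ending is decided after exposure to the in-clinic components. Endings at 4 weeks also come after the IVR and nurse steps, which are aimed at fill and adherence problems and reach one arm only. If EMC2 works as intended, it may change how many patients, and which kinds, remain under interview at 3 months. The 3-month knowledge contrast would then no longer compare the groups as randomised, except as far as the model repairs it.

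That repair has little to draw on. Ended patients contribute a baseline score and perhaps a 4-week score, but almost none has a 3-month score, so their later knowledge has to be borrowed from patients who kept taking the drug. The plan neither says that fill/take status enters the model nor says which 3-month quantity is meant for a patient who is no longer taking the drug. Because the drug list includes short-duration medicines (Section 29), one ended group can mix patients who never filled, stopped early or completed a course.

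**Working it through.** **1. The plan's own figure.** Inputs from Section 11.2: SD 28.4, 480 per arm, ICC 0.001, 80 per site at 3 months, 80% power, type I error 5% (two-sided assumed).

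- Design effect = 1 + (80 − 1) × 0.001 = 1.079.
- Detectable difference = 2.8016 × 28.4 × sqrt(2 × 1.079 / 480) = 5.33; power at 5.5 points = 82.3%.
- With 100 per site: design effect 1.099, difference 5.38, power 81.6%.

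The stated 5.5 points is reproduced, slightly on the cautious side. It rests on the 12 sites of Section 11.1; Sections 3.1, 3.2 and 19.1 say seven clinics. With 960/7 = 137.1 per clinic and the same ICC the difference is 5.47. The sample size is not the fault here; 5.5 serves only as a yardstick.

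**2. Bias left by the planned model.** Let sE and sC be the shares ended by rule in EMC2 and usual care. Let g3 be the 3-month knowledge gap (continuing minus ended patients), g0 the gap at the earlier visits, and ρ the within-patient correlation, taken as equal between all visits. A repeated-measures model under MAR corrects each arm by the regression on earlier scores:

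residual = (sE − sC) × (g3 − B × g0), where B = ρ with one earlier score (ended at baseline) and B = 2ρ/(1 + ρ) with two (ended at 4 weeks).

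The documents give none of these inputs. Assumed for illustration: sE = 25%, sC = 15%, g3 = g0 = 10 points, ρ = 0.5.

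| Case | Calculation | Residual | Share of 5.5 |
|---|---|---|---|
| One earlier score | 0.10 × (10 − 0.5 × 10) | +0.50 | 9% |
| Two earlier scores | 0.10 × (10 − 0.667 × 10) | +0.33 | 6% |

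**3. Sensitivity to the assumptions.**

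- Same share and same kinds of patients ended in both arms: 0.
- Rates reversed (15% vs 25%): −0.50 and −0.33.
- ρ from 0.3 to 0.7: 0.70 to 0.30 with one score, 0.54 to 0.18 with two.
- No earlier gap (g0 = 0): 0.10 × 10 = 1.0.
- g0 = 20 with one score: 0.10 × (10 − 10) = 0. g0 = 15 with two: 0.10 × (10 − 10) = 0.
- g0 = 20 with two scores: 0.10 × (10 − 13.33) = −0.33.

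A simulation with 2 million patients per arm (SD 28.4, ρ = 0.5) gave 0.55 and 0.32 for the two cases in the table, −0.52 and −0.36 with the rates reversed, 0.97 to 0.99 with no earlier gap, and 0.01 with equal rates. Its standard error is near 28.4 × sqrt(2/2,000,000) = 0.03, so it agrees with the formula.

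**The case against.** The best defence is that the planned analysis is not naive. It uses every available score. Endings follow a status reported at interview, so, given that status and the earlier scores, MAR could be reasonable. Section 11.1 names no missingness predictors at all, so leaving status out of the text does not exclude it. Section 9.4 already asks patients who have not filled or are not taking the drug about costs, side effects and risks. Section 29 describes outcomes from near the time of fill onward, and ended patients do contribute to that early part. All of this stands and lowers the weight of the point. It does not close the gap: nothing commits the analysts to using the status, and using it cannot supply 3-month scores that were never collected. One may also argue that knowledge of a discontinued drug is of no interest, but that is a different estimand, which the plan does not state.

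A reader might infer four stronger things that the documents do not support:

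- **A bias of 1.0 point, 18% of the target.** With the same assumed rates and gap, (0.25 − 0.15) × 10 = 1.0 is the error of a completers-only comparison. Section 11.1 does not plan one. The mixed model reaches 1.0 only if ended patients show no earlier gap.
- **Earlier scores always leave a remainder of the same sign.** Step 3 of the working shows that the residual can vanish or reverse.
- **A loss of power.** The 80% retention in Sections 11.1 and 11.2 may already include rule-based endings, so no precision loss is claimed.
- **Adverse drug event (ADE) data lost for everyone who stops.** Section 9.1 provides for early assessment "at an earlier interview if they state having already completed the course of medication", and Section 9.4 does so for finished medication. For other reasons for stopping, the measures brought forward under Section 22.4 might include it; the text does not say. This is a separate wording point and adds no weight to the knowledge concern.

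**Conclusion.** The point holds and should be fixed. What is certain is textual: interviews end on a post-randomisation status that the intervention targets, the outcome and time point that size the trial are lost in that group, and the missing-data plan does not mention the status. What is uncertain is the consequence. No stopping rates, knowledge gaps or correlations are given, so neither the size nor the sign of a bias can be derived. The 0.3 to 0.5 point in the working is an illustration for the planned model, resting on a 10-percentage-point difference in endings and an equal gap at every visit. It may be larger, smaller or reversed if the earlier gap differs from the 3-month gap. MAR is not shown to be false. The difficulty is that the status is not stated to be in the model, and that almost no one in that group has a 3-month value from which to learn.

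**What to change.** **Preferred.** Keep the scheduled 4-week and 3-month calls for all enrolled patients, with a short battery (knowledge, current use, ADE) for those not taking the drug, and analyse everyone as allocated. Report endings by arm and reason, separating never filled, stopped early and completed course, and building on the reasons already probed under Section 9.4. Include fill/take status in the missing-data model. Without the retained calls, that last step cannot recover 3-month knowledge.

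**If the calls cannot be kept.** State the estimand for 3-month knowledge in ended patients. Add a sensitivity analysis that shifts their unobserved scores over a stated range, for example 0 to −10 points, separately by arm.

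**Separate wording point.** State that the ADE questionnaire is given at every patient's final interview, and list the measures brought forward under Section 22.4.

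**Cost.** Short extra calls by the existing research assistants. If 20% are ended (assumed), 1200 × 0.20 = 240 patients, so 240 calls if all end at 4 weeks and 480 if all end at baseline. The upper figure is 480/24 = 20 calls a month spread over the 24-month recruitment period in Section 20.2. Consent already mentions up to three interviews (Section 28.1), but questions about a drug no longer taken add some burden, and the documents give no budget for call time. Under Section 22.4, patients whose final interview now comes early receive the second $20 then; with retained calls it would come later or could be lost, unless its timing is kept. Reporting by reason, ADE timing and the list of measures are wording changes.

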8. STUDY ENDPOINTS

8.1 Primary and secondary study endpoints.

The study’s primary endpoints are medication knowledge and medication behavior (fill, proper use, and actual use).

8.2 Primary or secondary safety endpoints.

The study’s safety endpoints include assessment of any Adverse Drug Events (ADE).

9. PROCEDURES INVOLVED

STU#: 00201638

9.1 Study design

We will conduct a 2-arm, randomized trial at one Alliance-affiliated federally qualified health center (FQHC) in Chicago, Near North Health Services Corporation, to evaluate the EMC2 intervention strategy compared to usual care.

We will assess patients' Rx knowledge and behavior at baseline, 4 weeks, and 3 months. Prevalence of ADEs and rate of their detection will be determined at 3 months or at an earlier interview if they state having already completed the course of medication. The fidelity and economic impact of the intervention will also be investigated via process and cost measures, in addition to patient and provider feedback. Results will determine effectiveness and identify any necessary modifications, guiding future dissemination efforts.

Study Arms:

Usual Care. Current usual care includes 1) variable physician and/or nurse counseling without any EHR notifications or counseling support; 2) no distribution of print medication information materials in Alliance clinics, and variable, limited distribution likely in pharmacies; 3) no active surveillance of medication use post-visits.

Intervention Arm: EMC2 Strategy. Following a patient's movement through a provider visit at one of the Near North clinics randomized to the intervention, the following five activities (described in more detail in 9.2) will occur:

- Provider counseling (prompted by provider medication alert)*
- Automated delivery of med guide summary*
- IVR follow-up phone assessment
- IVR lab report to clinic via EHR
- Nurse counseling (if warranted by lab report)

**Because the first two activities must occur at the time of the clinic visit, which is before we will have the opportunity to invite the participant to enroll in the study, those activities will occur for all patients prescribed a study medication at an intervention clinic, regardless of whether or not they subsequently enroll. (see last paragraph of 3.1)*

9.2 Description of the intervention

1. Provider Medication Alert: If a prescribing clinician attempts to place a new order or change an existing prescription for one of the study medications (Table 1), an EHR-generated alert will notify the provider that the medication requires patient counseling. This alert will contain a brief description of the top risks or side effects that patients may experience while taking this medication; this information is directly derived from the FDA-approved Medication Guide for the drug. The pop-up will also include an html link to the 1-page Med Sheet, which they can use to further inform their counseling.

2. Automated Delivery of Med Guide Summary: When the patient leaves an encounter and checks out, the medication order in Centricity will automatically cue printing of the 1-page Med Guide Summary.

STU#: 00201638

3. IVR Follow-Up Phone Assessment: One day after a patient's baseline interview (which will occur within 1-30 days post-visit), the patient will be prompted to call into the automated IVR system. The goal of the IVR call is to confirm patients' understanding and safe use of the prescribed high-risk medication they are taking, and to screen for any adverse drug events that may arise from having taken the medicine.

The call will investigate content areas that will be standard across all medications under study: 1) medication recognition, 2) medication fill (and fill barriers, if applicable), medication adherence (and adherence barriers, if applicable), perceived effectiveness, and side effects experienced. The IVR content was derived from the Med Guide Summaries. Patients are able to speak their responses as "yes", "no", or "do not know" or use their keypad.

To facilitate the call, patients will be sent (via text or phone call) a call-in number for the IVR system so that they are able to make the call at their convenience. The text with the call-in number will be sent on the day following the patient's baseline interview. (The day lag is needed so that the participant's medication data can first be uploaded to the IVR system in preparation for the call).

If subjects have not used the system after one day, a reminder text message, again including the call-in number, will be sent by the RA at Northwestern. If subjects have not used the system after two days, the RA at Northwestern will call the patient to remind them to call into the system and to ensure they have the call-in details.

4. Clinician Lab Reports. When a patient is flagged as having a medication-related concern based on the responses they give to the IVR system, the system will send an HL7 message to Alliance, which will appear as a 'lab report' in the patient's chart and sent to a centralized desktop at the clinic. The lab report will indicate the specific nature of the medication concern (e.g. fill concern, adherence concern, or safety concern), allowing the clinic staff to respond appropriately. Each clinic will be able to detail a reasonable response based on the type of concern reported. The default plan is that this role will be undertaken by nurses involved with care management responsibilities.

5. Nurse Counseling: Depending on the nature of the concern flagged, the IVR lab report will trigger the expectation for a clinic nurse to respond. Each FQHC can tailor their proper protocol for responding. During the IVR call, patients are told that issues will be reported to their clinic but that if they have concerns, they should call the clinic directly. The IVR system provides their clinic phone number before ending the call. This is done so that a patient is not left waiting for a response from the clinic when the clinic doesn't feel that the lab report warranted follow-up.

